14.9 Events exempt from being reported as AE/ SAEs

Progression of underlying disease

Disease progression and resultant death will be captured on the CRF. Adverse events including hospitalisation that are clearly consistent with disease progression will not be reported as individual AE/SAEs. Clinical symptoms of progression will only be reported as adverse events if the symptom cannot be determined as exclusively due to the progression of the underlying malignancy, or does not fit the expected pattern of progression for the disease under study.

Every effort should be made to document the objective progression of underlying malignancy. In some cases, the determination of clinical progression may be based on symptomatic deterioration. For example, progression may be evident from clinical symptoms, but is not supported by tumour measurements. Or, the disease progression is so evident that the Investigator may elect not to perform further disease assessments.

Death on study

Death due to disease under study is to be recorded on the Death CRF form, providing the death is not unexpected or if a causal relationship suspected. The Investigator must clearly state whether the death was expected or unexpected and whether a causal relationship to the study IMP or other protocol treatment intervention is suspected.

Elective admissions and supportive care

Elective admissions to hospital for patient convenience or for planned procedures or investigations or treatment as specified in this protocol and standard supportive care are not SAEs, and do not require SAE reporting. Hospital admission for the following supportive care procedures are considered standard for this patient group and should not be reported as SAEs:

- Non-emergency admission for feeding tube placement
- A visit to accident and emergency or other hospital department for less than 24 hours, that does not result in admission (unless considered an important medical or life-threatening event)
- Admissions as per protocol for a planned medical/surgical procedure
- Routine health assessment requiring admission for baseline/trending of health status
- Medical/surgical admission other than to remedy ill health and planned prior to entry into the study
- Admission encountered for another life circumstance that carries no bearing on health status and requires no medical/surgical intervention (e.g. lack of housing, economic inadequacy, caregiver respite, family circumstances, administrative reason)
- Admission for administration of anti-cancer therapy in the absence of any other SAEs

14.10 Informing Investigators of new safety information

Regular dose decision meetings will be held during which new safety information will be disseminated and discussed. Principal Investigators should attend such meetings, or send an appropriate representative.

Principal Investigators are responsible for briefing their study team and onward transmission to their R&D office as appropriate. The Trial Office or the Chief Investigator will ensure that all Investigators are kept informed in a timely manner, as new safety profile information becomes available.

14.11 Summary of trial safety reporting requirements

Event	DLT	SAE	AE,	/SAE
AE/SAE defined as Dose limiting toxicity (DLT)	Email SAE	reporting	Report in	Non-
Defined as per NCI CTCAE v4.03		n 24 hours	AE CRF	reportable
Grade ≥4 absolute neutrophil count (ANC) (<0.5 x 10^{9} /L) for >7 days	х		х	
Grade ≥3 febrile neutropenia (fever of unknown origin without clinically or microbiologically documented infection) (ANC <1.0 x 10 ⁹ /L, fever ≥38.5°C) lasting >3 days	x		х	
Infection (documented clinically or microbiologically) with grade 3 or 4	x		Х	

neutropenia (ANC <1.0 x 10 ⁹ /L)				
Grade \geq 3 thrombocytopenia (platelets <25 x 10 ⁹ /L)	x		v	
Clinically significant bleeding attributed to grade 3 thrombocytopenia or	^		X	
requiring platelet transfusion	х		х	
Grade ≥3 oesophagitis	x		х	
Grade ≥3 pneumonitis onset within 3 months of starting radiotherapy	X		X	
Grade \geq 3 nausea or vomiting not controlled by optimal outpatient anti-emetic	~		~	
treatment for ≥5 days	х		х	
Grade \geq 3 diarrhoea despite optimal outpatient anti-diarrhoeal medication use	x		x	
Any toxicity causing a delay of radiotherapy completion by greater than one				
week	х		х	
An elevation of ALT or AST >5 x ULN lasting 8 days or more	x		x	
A concurrent elevation of ALT or AST (>3 × ULN) and total bilirubin (>2 × ULN) in				
whom there is no evidence of biliary obstruction or other causes that can	x		х	
reasonably explain the concurrent elevation				
Other grade \geq 3 effects thought to be clinically significant and directly related to				
the combination of atovaquone with chemoradiotherapy	X		х	
	Email repo	rting form	Report in	Non-
Medically important events in the context of this trial	within 2	4 hours	AE CRF	reportable
Events believed to be possibly, probably or definitely related to treatment with		v	v	
Durvalumab rather than trial IMPs		Х	х	
AE/SAEs, showing associations and laboratory results	Email repo	rting form	Report in	Non-
AE/SAEs, abnormal assessments and laboratory results	within 2	4 hours	AE CRF	reportable
AE is life-threatening		Х	х	
AE requires in-patient hospitalisation or prolongs existing inpatient		x	x	
hospitalisation		^	^	
AE results in persistent or significant incapacity or disability		Х	x	
AE is a congenital anomaly or birth defect		Х	Х	
AE is any other medically important event		Х	x	
All other grade ≥3 AEs, assessments, abnormal laboratory results, if clinically significant		x	x	
All other grade <2 AEs, assessments, abnormal laboratory results, if clinically				
significant			х	
Grade ≥3 laboratory results not fulfilling safety reporting criteria		X1	X1	
Disease progression and death	Email repo	rting form	Report in	Non-
Disease progression and death	within 2	4 hours	AE CRF	reportable
Clinical symptoms, assessments or laboratory results associated with disease progression				x
Hospitalisation for disease progression				х
Non-emergency admission for feeding tube placement				X
A visit to accident and emergency or other hospital department for less than 24				~
hours, that does not result in admission (unless considered an important				х
medical or life-threatening event)				~
Admissions as per protocol for a planned medical/surgical procedure				х
Routine health assessment requiring admission for baseline/trending of health	1	1		
status				х
Medical/surgical admission other than to remedy ill health and planned prior to	1	1		
entry into the study				х
Admission encountered for another life circumstance that carries no bearing on				
health status and requires no medical/surgical intervention				x
Admission for administration of anti-cancer therapy in the absence of any other				
SAEs				х
Death	1	X ²	X ³	

¹ If a lab result is categorised as Grade 3 or 4 but did not fulfil the safety reporting criteria for an SAE (asymptomatic, not life threatening, no intervention), it is the clinician's decision whether to report the event. If the event is not reported the reason why should be documented in the patient notes.

² If death is possibly related directly to atovaquone or the combination of atovaquone + radiotherapy +/- chemotherapy.

³ Providing the death is not unexpected or if a causal relationship is not suspected. The investigator must clearly state whether a causal relationship to atovaquone + radiotherapy +/- chemotherapy is suspected, and if so, whether the death was expected or unexpected.

15 PREGNANCY

Pregnancies (in a participant or partner) occurring while participating in this trial require expedited reporting. A pregnancy form should be completed, scanned and emailed to the Trial Office within the same timelines as an SAE. All reported pregnancies should be followed and the outcome reported using the same form. If the outcome of the pregnancy meets any of the criteria for seriousness, it must also be reported as an SAE. Examples of pregnancy outcomes that are SAEs include reports of:

- Congenital anomalies or developmental delay, in the foetus or the child
- Foetal death and spontaneous abortion
- Suspected adverse reactions in the neonate that are classified as serious

Women who become pregnant should be withdrawn from trial treatment immediately. Any pregnancy occurring up to the patient's last study visit (i.e. in the six months following CRT) should be reported by the participant to the Trial Office.

16 DEFINING THE END OF TRIAL

For this study the end of the trial is defined as: "The last visit of the last patient undergoing the trial (LPLV)". The study will be stopped when:

- The stated number of patients to be recruited is reached.
- The stated objectives of the study are achieved.

The Sponsor and the Chief Investigator reserve the right to terminate the study earlier at any time. In terminating the study, they must ensure that adequate consideration is given to the protection of the participants' best interests.

17 STATISTICAL CONSIDERATIONS

17.1 Study design

This is a phase I, single arm, open label, two-centre study. The primary objective is to identify the MTD, and thus RPTD, of atovaquone when combined with concurrent CRT in NSCLC using a Bayesian TiTE-CRM design.

The CRM is a model-based method for finding the maximum tolerated dose (MTD) under the defining monotonicity assumption which posits that toxicity increases monotonically with increasing dose, and that efficacy also increases with increasing dose. The objective is to find the dose with a probability of experiencing a Dose Limiting Toxicity (DLT) close to a pre-specified target toxicity level. The TiTE-CRM is a modified version of the CRM that allows late-onset toxicities to be accounted for without fully observing a patient before recruiting the next and is therefore particularly advantageous for radiotherapy trials where toxicities are often observed later than in studies using systemic therapy alone. A major advantage of the TiTE-CRM is the fact that it uses all current accumulated information to decide which dose to assign the next patient. A further advantage of this design is that it will be able to include partial information on patients who could not be formally evaluated for DLTs due to withdrawal, treatment discontinuation or death, that is unrelated to treatment within the DLT assessment period (from week-2/-3 to three months post-CRT). In addition, the method results in shorter study duration as it is not necessary for a patient to be observed for the full observation period before recruiting the next patient, and also more patients are treated close to the MTD.

Toxicity will be scored according to NCI CTCAE v4.03 with DLT definition as stated in Section 9. The trial aims to identify the MTD which is the dose associated with no more than 48% DLT rate (target toxicity level). This is based on the fact that standard concurrent CRT for NSCLC is often associated with a significant Grade \geq 3 toxicity rate. Average rates of Grade \geq 3 oesophagitis are in the region of 25%, although reported rates are variable and can be as high as 48%. In addition, rates of Grade \geq 3 pneumonitis as high as 32% have been reported and haematological toxicity when using platinum-doublet chemotherapy can also be significant in this patient population [22]. The atovaquone treatment schedule lasts for up to 9.5 weeks, with patients followed up at the end of the DLT assessment period (at three months post-CRT). An additional follow-up occurs a further three months later (at six months post-CRT), to provide a total trial observation window of up to 38 weeks.

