9 DOSE LIMITING TOXICITY

9.1 Definition of a Dose Limiting Toxicity

All patients who have received at least one dose of atovaquone will be evaluable for DLTs.

DLTs are defined as any of the following occurring between the start of trial treatment until three months post CRT, and assessed by the Principal Investigator as possibly, probably or definitely related to atovaquone and/or to chemoradiotherapy. If an event is believed to be possibly, probably or definitely related to treatment with Durvalumab rather than trial IMPs, it may be reported as an SAE rather than a DLT.

DLTs will be defined as per NCI CTCAE v4.03 and include:

- Grade \geq 4 absolute neutrophil count (ANC) (<0.5 x 10⁹/L) for >7 days
- Grade ≥3 febrile neutropenia (fever of unknown origin without clinically or microbiologically documented infection) (ANC <1.0 x 10⁹/L, fever ≥38.5°C) lasting >3 days
- Infection (documented clinically or microbiologically) with grade 3 or 4 neutropenia (ANC <1.0 x 10⁹/L)
- Grade \geq 3 thrombocytopenia (platelets <25 x 10⁹/L)
- Clinically significant bleeding attributed to grade 3 thrombocytopenia or requiring platelet transfusion
- Grade ≥3 oesophagitis
- Grade ≥3 pneumonitis onset within 3 months of starting radiotherapy
- Grade ≥3 nausea or vomiting not controlled by optimal outpatient anti-emetic treatment for ≥5 days
- Grade ≥3 diarrhoea despite optimal outpatient anti-diarrhoeal medication use
- Any toxicity causing a delay of radiotherapy completion by greater than one week
- An elevation of ALT or AST >5 x ULN lasting 8 days or more
- A concurrent elevation of ALT or AST (>3 × ULN) and total bilirubin (>2 × ULN) in whom there is no evidence of biliary obstruction or other causes that can reasonably explain the concurrent elevation
- Other grade ≥3 effects thought to be clinically significant and directly related to the combination of atovaquone with chemoradiotherapy

Dose limiting toxicities must be reported within 24 hours of the site becoming aware using the SAE form (even if the event does not meet the definition of an SAE). Scan the form and email as an attachment to [contact].

See section 14 for safety reporting procedures.

DLTs will be processed to support dose decisions according to procedures detailed in Section 17 and the separate Protocol Decision Point Plan.

10 **OTHER TREATMENTS (NON-IMPS)**

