13.4 Other definitions of outcome

Toxic death:Any death to which drug toxicity is thought to have a major contribution.Early death:Death during the first three weeks of treatment that is not a toxic death.

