17.2 The TiTE-CRM model

A two-parameter Bayesian logistic model with weak priors will be used. The priors are calibrated to ensure the model provides sensible recommendations early in the trial. With this model we can obtain a distribution for the probability of DLT rate given a specific dose d based on all available data. This is a posterior probability distribution for dose d. We write P(T>0.48 | Data, dose = d) to mean the posterior probability that the DLT rate is greater than 48% on dose d, given the data observed so far.

At each dose decision (to assign a dose to the next patient), data for patients who have completed the DLT assessment period or experienced a DLT will contribute full information to this model. Only partial information is known for patients who are currently on trial, within the DLT assessment period, or have stopped treatment in the DLT assessment period for reasons other than a DLT. This partial information contributes to the model, weighted proportionally to the observed portion of their toxicity time window and treating them as not experiencing a DLT.

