6.2 Analysis Methods

Primary analysis

To determine the maximum tolerated dose (MTD), and therefore recommended phase II dose (RPTD), of atovaquone when combined with radical concurrent chemoradiotherapy

All trial patients who received at least one dose of atovaquone will be included in the primary analysis. The same analysis is used during dose escalation as for the final analysis.

The analysis will follow the TiTE-CRM. A two-parameter logistic model will be used to model the relationship between dose and toxicity i.e. the dose toxicity curve (DTC). Dose recommendations following the first two evaluable patients will be made using all current toxicity data as follows:

- Data for patients who have completed the DLT assessment period or experienced a DLT will contribute full information to this model.
- Data for patients who have not completed the DLT assessment period will contribute partial information to the model, weighted proportionally to the observed portion of their time window, and treating them as not experiencing a dose limiting toxicity. The weight function is defined in the equation below as w_i.

There are 4 atovaquone doses which are coded x = 1:4. Assuming dose 1 is the reference dose, d^* , we have treated J patients with dose x_j , j = 1, ..., J, then we model the probability of a DLT occurring using the weighted likelihood given by

$$L(\theta) = \prod_{j=1}^{J} \left[\theta_{x_j} * w_j \right]^{y_j} \left[(1 - \theta_{x_j}) * w_j \right]^{1 - y_j}$$

where

 $y_{j} = \begin{cases} 1 \text{ if dlt occured} \\ 0 \text{ if no DLT} \end{cases}$ $g\left(\theta_{x_{j}}\right) = logit\left(\theta_{x_{j}}\right) = log(\alpha) + \beta log\left(\frac{x_{j}}{d^{*}}\right) \text{ this is the unweighted two-parameter logistic model}$ $w_{j} = \begin{cases} 1 \text{ if } y_{j} = 1 \\ \min\left(1, \frac{u_{j}}{T_{i}}\right) \text{ if } y_{j} = 0 \end{cases}$

 u_j = time patient j has been followed for and T_j = total DLT window for patient j = pre-specified run-in time + 45 days + 84 days (note: as patients are followed up in the trial beyond the DLT observation period, u_j can exceed T_j in which case the weight for patient j in the model will still be 1).

Further detail on the chosen prior distributions for the parameters and simulation results is described in Appendix 1.

See Neuenschwander, Branson and Gsponer (2008) and Cheung YK and Chappell R (2000) for descriptions of the model

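### A treatment-related death that falls outside the listed DLT items would be modelled as DLT-free, because Protocol 17.2 and SAP 6.2 lack the relatedness condition that Protocol 17.1 attaches to partial information

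*Protocol*

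**What the plan says.** Protocol 17.1 lists, as an advantage of the TiTE-CRM, that it can use partial information on "patients who could not be formally evaluated for DLTs due to withdrawal, treatment discontinuation or death, that is unrelated to treatment".

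Protocol 17.2 gives the working rule. Partial, non-DLT weight goes to patients still inside the window and to those who "have stopped treatment in the DLT assessment period for reasons other than a DLT". SAP 6.2 is broader: "Data for patients who have not completed the DLT assessment period will contribute partial information to the model, weighted proportionally to the observed portion". Neither mentions death or relatedness. SAP 6.2 uses the same model at every dose decision and at the final analysis.

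Protocol 9.1, repeated in SAP Appendix 4, defines a DLT as a listed event judged "possibly, probably or definitely related to atovaquone and/or to chemoradiotherapy". No item names death. Several items are open-ended at grade 3 or above. Others carry conditions, for example "Infection (documented clinically or microbiologically) with grade 3 or 4 neutropenia", and pneumonitis counts only if it starts within 3 months of starting radiotherapy. The last item is "Other grade ≥3 effects thought to be clinically significant and directly related to the combination of atovaquone with chemoradiotherapy".

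Protocol 13.4 defines toxic death as "Any death to which drug toxicity is thought to have a major contribution" but does not link it to DLT. The Death row of the table in Protocol 14.11 appears to be marked for SAE and AE reporting and not as a DLT, although the layout of that table is damaged in the copy reviewed.

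**The concern.** The 17.1 qualifier implies that a treatment-related death is not the kind of incomplete follow-up that should be treated as DLT-free. The rules that feed the model do not carry that qualifier, so everything depends on whether the fatal event meets a listed item.

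The catch-all does not close the gap. The header of 9.1 needs only a possible relation to atovaquone or to chemoradiotherapy. The catch-all needs a direct relation to the combination. A death thought possibly due to cisplatin or to radiotherapy alone can satisfy the header and match no item.

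Such a death would pull the estimated DLT rate down when it should push it up, which biases the MTD upward. It could also leave the 450 mg safety stop untriggered. And the patient could formally serve as the qualifying patient for escalation, since the four criteria ask for no DLT and are silent on death.

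**Working it through.** The documents give no figure on this point to reproduce. The check is a comparison of the rules, then an illustration.

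**1. Deaths that can fall through.** Each example is assumed to be judged possibly or probably related under the 9.1 header, but not directly related to the combination.

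- Pulmonary embolism: no listed item.
- Lung infection without grade 3 or 4 neutropenia: fails the infection item.
- Late pneumonitis: from radiotherapy start the DLT window runs 45 + 84 = 129 days (SAP 6.2). The item covers about 91 days, taking 3 months as 13 weeks. The uncovered tail is 129 − 91 = 38 days, or 38/129 = 29%.

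Protocol 12.5 lists lung infection at 22% and pulmonary embolism at 7%. These are event rates, not death rates. They show only that such events are expected with this chemoradiotherapy.

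**2. Score received.** By SAP 6.2, y = 0 and w = u/T, with T = run-in + 45 + 84 days. For a 14-day run-in, T = 143. Death just after three weeks of radiotherapy gives w = 35/143 = 0.24. Death on day 49 gives w = 49/143 = 0.34.

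**3. Escalation criteria.** If the 75% atovaquone criterion refers to the whole 59-day course, a patient at day 35 has 35/59 = 59% and does not qualify. The threshold is reached at 0.75 × 59 = 44 days. If it means dose to date, it can be met earlier. The documents do not give the denominator.

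**4. Effect on the model at 450 mg.** SAP Appendix 1, which holds the priors, was not available, so five priors are assumed. With dose 1 as reference, log(x/d*) = 0, so the dose-1 posterior depends only on log α when all data are at dose 1. The likelihood is θ for a DLT and 1 − wθ otherwise. The death is on day 49 (w = 0.34). Each cell shows scored non-DLT → scored DLT.

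| Prior median at 450 mg, SD of log α | Two clean + death: mean | One clean, one DLT + death: mean | One clean, two DLTs + death: mean | Same data: P(rate > 0.48) |
|---|---|---|---|---|
| 0.35, 1 | 0.26 → 0.35 | 0.39 → 0.48 | 0.47 → 0.54 | 0.48 → 0.65 |
| 0.30, 1.5 | 0.19 → 0.33 | 0.39 → 0.52 | 0.51 → 0.60 | 0.55 → 0.74 |
| 0.25, 1 | 0.20 → 0.30 | 0.33 → 0.42 | 0.41 → 0.49 | 0.33 → 0.52 |
| 0.30, 2 | 0.16 → 0.34 | 0.41 → 0.57 | 0.55 → 0.65 | 0.61 → 0.80 |
| 0.40, 1.5 | 0.23 → 0.37 | 0.44 → 0.56 | 0.55 → 0.63 | 0.62 → 0.79 |

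The mean moves by about 7 to 15 points, and by up to 18 under the vaguest prior (SD 2). In the last column the 0.7 limit is crossed under three of the five priors, and only when the death counts as a DLT.

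As printed, SAP 6.2 multiplies (1 − θ) by w, so w cancels and the death would count as a full DLT-free patient. That is a separate matter; the table uses the usual form.

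**5. At full size.** In simulated 20-patient trials (two assumed priors, three assumed toxicity curves), rescoring one patient from non-DLT with w = 0.5 to DLT raised the posterior mean at that dose by 3 to 4 points and lowered the declared MTD in 12% to 26% of trials. These figures are conditional on such a death having occurred.

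**6. How often.** With an assumed toxic-death rate q per patient, P(at least one in 20) = 1 − (1 − q)^20 = 18%, 33% and 64% for q = 1%, 2% and 5%. The deaths at issue are a subset, so their probability is lower.

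**The case against.** Four points can fairly be made against this.

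- **17.1 is descriptive.** It states an advantage of the design and never says that only unrelated deaths give partial information. A reader might infer a flat prohibition that 17.2 and the SAP break. The text does not go that far. What stands is that its qualifier has no effect under the rules actually applied.
- **Most toxic deaths may already count.** A reader might infer that any toxic death is scored DLT-free. That is not supported: fatal oesophagitis, early pneumonitis, diarrhoea or prolonged febrile neutropenia can meet an open-ended item, and a death attributed directly to the combination meets the catch-all. The gap is the remainder. It also affects non-fatal severe events of the same kinds, because its root is the catch-all's attribution wording.
- **Escalation is guarded.** A reader might infer that such a death would release escalation by itself. It would not. The model must recommend the higher dose, leaving 450 mg needs 12 weeks of data on at least one participant, the TMG reviews every recommendation, the SRC can be convened, and SAP 6.4 reruns each interim counting patients with insufficient follow-up as DLTs. The deceased patient matters only if nobody else at that dose qualifies.
- **The separate Protocol Decision Point Plan may contain a rule.** It was not available for this review.

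The safeguards reduce the escalation risk. They do not alter the primary scoring. SAP 6.4 is a sensitivity analysis and its toxic scenario is limited to interims, while the MTD is defined as the dose from the final model.

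**Conclusion.** The point holds in a limited form. A death inside the DLT window that is judged related under the 9.1 header, meets no listed item and is not attributed directly to the combination would enter the interim and final models as y = 0 with weight u/T. This sits badly with 17.1, and the written escalation criteria would not exclude the patient.

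The consequence can be material when data are few: about 7 to 15 points at 450 mg (18 under the vaguest prior), and a different answer from the stopping rule in one plausible data set under some priors. The likelihood of meeting the problem is unknown. It is below the 18%, 33% and 64% given for any toxic death at the assumed rates. All sizes rest on assumed priors, an assumed day of death and small hypothetical data sets. The inconsistency in the rules does not depend on those assumptions.

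**What to change.** Reconcile Protocol 9.1, 17.1, 17.2 and the Death row of 14.11 with SAP 6.2 and Appendix 4. The aligned text should:

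- say that a death in the DLT window judged related to trial treatment under the 9.1 header is not entered as a DLT-free partial observation, consistent with 17.1;
- keep the Durvalumab exception in 9.1 explicit, since Durvalumab may start before the window closes;
- state whether a patient who died of a related cause can satisfy the escalation criteria;
- carry the same rule into the Protocol Decision Point Plan.

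No new data are needed, because adverse-event relatedness and any suspected causal link for a death are already recorded. The cost is a few lines of text. They touch the primary endpoint, so an amendment may be required, and the observed DLT rate may be slightly higher. Simulations need rerunning only if they modelled deaths explicitly.
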